10.1. Point of Enrollment

Subjects will only be enrolled in this study if they meet all eligibility criteria and provide written informed consent. If a subject doesn't meet all eligibility criteria prior to the implant procedure (e.g., no attempt of Rally CRT-P implant is planned) the subject will be withdrawn from the study; any points of ineligibility must be clearly documented in the enrollment/screening log. These subjects will be considered consent ineligible as discussed in Section 10.3, and will not count towards the enrollment ceiling. Any subject that signs consent and meets all Inclusion Criteria and does not meet any Exclusion Criteria will be enrolled followed in the study. If a subject signs consent and meets all eligibility criteria but does not receive the Rally CRT-P implant (for example: anesthesia complications, Visionist CRT-P device was finally not implanted, etc.), the subject will be followed for 30 days for safety reasons and will then be withdrawn from the study (Section 9.1).

10.2. Withdrawal

All subjects enrolled in the clinical study (including those withdrawn from the clinical study or lost to follow-up) shall be accounted for and documented. If a subject withdraws from the clinical investigation, the reason(s) shall be reported. If such

withdrawal is due to problems related to investigational device safety or performance, the Investigator shall ask for the subject's permission to follow his/her status/condition outside of the clinical study.

Reasons for withdrawal include physician discretion, subject choice to withdraw consent, loss to follow-up, or death. While study withdrawal is discouraged, subjects may withdraw from the study at any time, with or without reason, and without prejudice to future treatment. All applicable case report forms should be completed up to the point of subject withdrawal. Subjects who are "lost-to-follow-up" should have 3 documented failed phone call attempts to contact the subject as well as a certified letter sent to the subject without a response prior to study withdrawal or termination. Sites should also contact their municipal registries (as available in the geography) to determine if the subject may have expired. A death note will need to be provided together with the Serious Adverse Event (SAE) event description on the Adverse Event (AE) form. Additional data may no longer be collected after the point at which a subject has been withdrawn from the study or withdraws his/her consent, for whatever reason. All open AEs should be closed or documented as chronic or continuing at the end of the study. Data collected up to the point of subject withdrawal may be used. A Study Withdrawal Case Report Form (CRF) should be completed at this time. A retrospective cancelling of subject data collection should be expressed explicitly by the subject so that all data can be removed from the database.

Subjects who do not receive an LV lead or an atrial lead will be followed until the Latitude based Close-out.

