Statistical Test Method	
Sample Size Methodology:
 
 • Sample size for the primary safety endpoint was calculated using exact binomial methods for comparison of a single proportion to a performance goal. • Sample size for the primary effectiveness endpoint was calculated using one-sample t-test methodology for comparison of a single mean to a performance goal. 
Analysis Methods:
 
 • The DRCFR from implant will be calculated as the proportion of actively enrolled subjects without a device-related complication through 3 months after implant. The null hypothesis will be rejected and the endpoint considered met if the lower one-sided 95% confidence bound for the proportion of subjects with no device-related complication is greater than 87.5%. • Regarding mean LV pacing threshold at 3 months post-implant, the null hypothesis will be rejected and this endpoint considered met if the upper one-sided 95% confidence bound for the mean LV pacing threshold at 3-months is less than 2.5V. 
Further details on analytical methods can be found in Section 12.0 of the CIP.

Sample Size Parameters	
DRCFR through 3 months post-implant: 62 subjects. Sample size was calculated assuming a 97.5% DRCFR, a performance goal of 87.5%, one-sided alpha level of 0.05, 80% power, and 20% attrition.
 
Mean LV pacing threshold at 3 months post-implant: 45 subjects. Sample size was calculated assuming a mean (\pm standard deviation [SD]) LV pacing threshold of $1.9 \pm 1.2V$, a performance goal of 2.5V, one-sided alpha level of 0.05, 90% power, and 20% attrition.
 
Based on the above sample size calculations, the minimum required sample size to statistically power the primary endpoints is 62 subjects.

3. Table of Contents

1. TITLE PAGE	1
2. CLINICAL INVESTIGATION PLAN SYNOPSIS	4
3. TABLE OF CONTENTS.....	10
3.1. Table of Figures.....	13
3.2. Table of Tables	14
4. INTRODUCTION	15
5. DEVICE DESCRIPTION.....	18
5.1. Ingenio 2 Cardiac Resynchronization Therapy Pacemakers.....	18
5.1.1. PaceSafe.....	21
5.1.2. Post-Operative System Test.....	21
5.1.3. Atrial Arrhythmia Reports	22
5.1.4. ECG/EGM Snapshots	22
5.1.5. Leads.....	22
5.1.6. ZIP Telemetry	22
5.1.7. Programming System.....	22
5.2. Ingenio 2 CRT-P Indications for Use	23
5.3. Ingenio 2 CRT-P Contraindications.....	24
6. STUDY OBJECTIVE	24
7. ENDPOINTS	24
7.1. Primary Safety Endpoint.....	24
7.2. Primary Effectiveness Endpoint	24

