12.1.1.2. Statistical Methods

When the final study subject reaches the 3 Month required follow-up visit, the primary safety analysis will be performed based on exact binomial methods for the estimation of the DRCFR, including the exact lower one-sided 95% confidence bound. Subjects that die/withdraw or are lost-to-follow-up prior to the 3-month endpoint evaluation ($\leq 91 + 21$ days post-implant or post-implant attempt) and have not experienced device-related complications will be excluded from the analysis. The sample size was adjusted to account for up to 20% attrition to ensure there would be a sufficient number of evaluable subjects through 3-months.

The primary safety endpoint will evaluate the DRCFR through 3-months post-implant (or implant attempt), calculated using exact binomial methods. The null hypothesis will be rejected and the endpoint considered met if the lower one-sided 95% confidence bound for the DRCFR at 3-months is greater than 87.5%.

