12.3. Sample Size

The minimum required sample size to evaluate the primary endpoints and account for up to 20% attrition is 62 (Table 12-1).

Table 12-1: Endpoint Sample Size Estimates

Endpoint	Measurement	Hypotheses ¹	Expected Performance	Power	Number of Subjects	
					needed for analysis	to be enrolled for ≤ 20% attrition
Primary Safety Endpoint	DRCFR from 0 to 3 months	$H_0: \text{DRCFR} \leq 87.5\%$ $H_A: \text{DRCFR} > 87.5\%$	97.5%	80%	49	62
Primary Effectiveness Endpoint	LV pacing threshold at 3 months	$H_0: \text{mean} \geq 2.5\text{V}$ $H_A: \text{mean} < 2.5\text{V}$	$1.9 \pm 1.2\text{V}$	90%	36	45

¹ Hypothesis test based on a one-sided alpha level of 0.05.

LV=left ventricular; DRCFR=device-related complication free rate

Sample sizes were calculated employing exact binomial methods (primary safety endpoint) and one-sample t-test methodology (primary effectiveness endpoint) in nQuery 6.0.

The following assumptions were used for the calculation of sample sizes:

- Primary Safety Endpoint
 - Expected DRCFR = 97.5% (determined from prior comparable BSC devices)
 - Performance goal = 87.5% (clinically accepted delta of 10%, subtracted from expected DRCFR)
 - Test significance level (α) = 0.05 (one-sided)
 - Power = 80%
- Primary Effectiveness Endpoint
 - Expected mean (\pm standard deviation [SD]) LV pacing threshold = $1.9 \pm 1.2\text{V}$ (based on prior BSC LV lead performance)
 - Performance goal = 2.5V (used in prior BSC led approval studies)
 - Test significance level (α) = 0.05 (one-sided)
 - Power = 90%

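### A device-related complication that occurs after a device-reason withdrawal, but within the 3-month window, has no route into the DRCFR

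*Combined protocol and SAP*

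**What the plan says.** Section 10.2 lists physician discretion, withdrawal of consent, loss to follow-up and death as reasons for withdrawal, and requires the reason to be reported. It singles out subjects who leave because of a device safety or performance problem. For them the investigator asks for "permission to follow his/her status/condition outside of the clinical study". The same section says "Additional data may no longer be collected after the point at which a subject has been withdrawn from the study", extends this to withdrawal of consent, and applies it whatever the reason. Data gathered before withdrawal may be used.

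Section 12.1.1.2 provides that subjects who die, withdraw or are lost before the 3-month evaluation "and have not experienced device-related complications will be excluded from the analysis". Section 12.4.1 repeats the exclusion. The cut-off is 91 + 21 days in 12.1.1.2 and 91 days in 12.4.1.

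Under Section 12.1.1 a device-related complication needs an outcome: death, serious injury, invasive correction or permanent loss of device functions, assessed as related to the device. No section treats device-reason leavers differently from other leavers, and no sensitivity analysis for excluded subjects is planned.

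**The concern.** A device problem can lead a subject to leave before it has produced one of the outcomes that define a complication. If the outcome follows after withdrawal but within 3 months of implant, Section 10.2 keeps it out of the study data and Section 12.1.1.2 removes the subject from numerator and denominator alike.

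Excluding leavers is harmless when leaving is unrelated to the endpoint. Here the plan itself identifies a group whose reason for leaving is the device, and handles them as if the reason carried no information. If their complication rate is higher than that of the subjects who stay, the DRCFR is overstated and the 87.5% goal is easier to meet. The 20% attrition allowance protects the number of evaluable subjects and does nothing about this bias.

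**Working it through.** **Inputs.** From Section 12.3 and the synopsis: expected DRCFR 97.5%, performance goal 87.5%, one-sided alpha 0.05, target power 80%, 49 subjects for analysis, 62 enrolled with up to 20% attrition. From Section 12.1.1.2: success if the exact lower one-sided 95% bound exceeds 87.5%. The number of device-reason leavers, w, is not in the documents and is assumed below.

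**The plan's own figure.** With n = 49 and X complications, success requires X ≤ 2.
- Exact alpha = P(X ≤ 2 | n = 49, rate 0.125) = 0.046.
- Power = P(X ≤ 2 | n = 49, rate 0.025) = 0.876.
- At n = 48 only X ≤ 1 passes and power is 0.662, so 49 is the smallest n that reaches 80%.
- 49 / (1 − 0.20) = 61.25, rounded up to 62.

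Both stated figures reproduce. The plan therefore allows 62 − 49 = 13 leavers of all kinds.

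**Exact bounds.** With f failures in n, the lower bound is the 5th percentile of a Beta(n − f, f + 1) distribution (Clopper-Pearson). Take 49 other evaluable subjects and add w device-reason leavers as failures:

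| Recorded complications in 49 | Leavers excluded, as planned | w = 1 | w = 2 | w = 3 |
|---|---|---|---|---|
| 0 | 0/49: 94.1%, met | 1/50: 90.9%, met | 2/51: 88.2%, met | 3/52: 85.8%, missed |
| 1 | 1/49: 90.7%, met | 2/50: 87.9%, met | 3/51: 85.5%, missed | missed |
| 2 | 2/49: 87.7%, met | 3/50: 85.2%, missed | missed | missed |

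Three failures miss the goal up to n = 59 (3/59: 87.4%) and meet it at n = 60 (3/60: 87.6%). So with 2 recorded complications, a single added failure reverses the result when there are 49 to 58 other evaluable subjects.

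**How likely each row is.** At the expected 97.5%, the probabilities of 0, 1 and 2 complications in 49 are 0.289, 0.363 and 0.224. The row in which one leaver decides the result has a probability of about 22%. The two rows in which one leaver changes nothing total about 65%.

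**Effect on type I error, under an assumption.** Let the true DRCFR be 87.5%. Suppose each subject who would have a complication withdraws first with probability q and is excluded, and nobody else leaves. The complication-free rate among those analysed becomes 0.875 / (0.875 + 0.125(1 − q)). At q = 0.20 this is 0.875 / 0.975 = 89.7%. Averaging the exact test over the random number analysed gives:

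| Subjects at risk | q = 0 | q = 10% | q = 20% |
|---|---|---|---|
| 62 | 4.0% | 6.9% | 10.4% |
| 49 | 4.6% | 4.9% | 5.9% |

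The documents give no value for q. The table shows direction and sensitivity and is not a forecast.

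**The case against.** **Leavers with a complication are not dropped.** A reader might infer that everyone who leaves over a device problem disappears from the DRCFR. The text does not say so: the exclusion covers only those without a device-related complication so far. The complication definition is also broad. The notes to Table 19-1 count intravenous medication as invasive intervention, so many problems serious enough to cause withdrawal may already have counted. This stands and limits the point to complications that arise after withdrawal.

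**The plan keeps subjects in.** Withdrawal is discouraged, re-implant and revision are study procedures with their own data collection (Section 11.5), and subjects who do not receive an LV or atrial lead are still followed to close-out. It would be wrong to read the plan as taking subjects off study when a revision is needed. These provisions make the case rarer but do not cover a subject who has already left. Section 11.9 lets a subject with an ongoing device-related event be asked to stay enrolled, but only at study completion. Section 10.2 also asks that open adverse events be closed or documented as continuing at the end of the study. That sentence is ambiguous next to the bar on further data and gives no route into the DRCFR.

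**The direction is not certain.** Exclusion also removes leavers who would have stayed complication-free. That lowers n and makes the goal harder: 3/60 passes while 3/49 (84.9%) fails. This stands. The bias favours success only if these leavers have more complications than those who stay. That is plausible given why they left, but the documents do not establish it.

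**Conclusion.** The point holds in a limited form. For a device-reason leaver with no complication recorded before leaving, Sections 10.2, 12.1.1.2 and 12.4.1 together exclude the subject and leave a later complication within the window unable to count. The exclusion is potentially informative.

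Its size depends on unknowns. The number of such leavers is not given and may be zero. A reader might infer that one of the 13 permitted leavers is enough to overturn the result. That needs 2 complications already recorded, 49 to 58 other evaluable subjects, and a leaver who is in fact a failure. With 1 or 0 recorded in 49, it takes two or three such leavers.

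A reader might also infer from the provision on retrospective cancellation in Section 10.2 that a complication already counted could be erased. That requires the subject's explicit request, and the section requires all subjects to be accounted for. It is too speculative to press.

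The gap is worth closing because it bears on the primary safety claim and costs little to close.

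**What to change.** 1. In Section 10.2, for subjects withdrawn without withdrawing consent to data use, and for device-reason leavers who give permission, record device-related complications in the eCRF through the 3-month endpoint. In Section 12.1.1.2, count these complications as failures in the DRCFR. Reconcile the cut-off between 12.1.1.2 (91 + 21 days) and 12.4.1 (91 days) so that the collection window is defined.
2. In Section 12.1.1.2, keep the primary exclusion for device-reason leavers whose 3-month status remains unknown, and pre-specify a sensitivity analysis that counts each of them as a failure. They should not be retained as complication-free. That would move 2/49 (87.7%) to 2/50 (87.9%) and make the result more favourable.

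The cost is wording in two sections, a little extra data collection and one table. The reason for withdrawal is already reported. The DRCFR may come out slightly less favourable. The sample size does not change.

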10.3. Subject Status and Classification

Consent ineligible subject

A study subject who has signed informed consent but is found to not meet eligibility criteria will be considered a consent ineligible subject and will not count towards the enrollment ceiling. There are no follow-up or AE reporting requirements for consent ineligible subjects. The original signed Informed Consent must be maintained in the center's administrative file.

Active enrolled subject

A study subject who meets the eligibility criteria as per Section 9.2 and Section 9.3 and has signed and dated the Subject ICF is considered actively enrolled in the study. These subjects are followed in accordance with the CIP follow-up schedule and included in the foreseen study analysis. The original signed Subject ICF and any applicable documentation must be maintained in the center's subject file. All applicable eCRFs per the CIP must be completed.

10.4. Enrollment Controls

The study is planned to enroll a maximum of 30 device replacements, and a maximum of 10 subjects with a known indication for rate adaptive pacing which doesn't allow non-rate adaptive pacing between pre-discharge and one month follow up.

Each center may enroll up to a maximum of 20 Rally CRT-P study subjects in order to mitigate any bias from a single center in the final study analysis.

If a center wishes to exceed these limits, the center must obtain prior approval from the sponsor or sponsor's delegated representative.

Once 62 subjects have been enrolled and registered in the trial database, all centers will be informed that enrollment has closed. After closure of enrollment has been communicated, centers must obtain approval from the sponsor or the sponsor's delegated representative for all remaining subjects who are consented but not implanted or enrolled into the study database.

11. Study Methods

11.1. Data Collection

Details for data collection are shown in Table 11-1. Data collection will take place at the following time points:

- Required visits
 - Enrollment and Consenting Clinic Visit (\leq 30 days prior to implant procedure; required)
 - Implant Procedure (Day 0; all future follow ups based on this date; required)
 - Pre-Discharge Clinic Visit (after pocket closure 0-5 days post-implant procedure; required)
 - 1 month visit ($30 \text{ days} \pm 15 \text{ days}$ post-implant procedure; required)
 - 3 month Clinic Visit ($91 \pm 21 \text{ days}$ post-implant procedure; required)
 - Latitude-based Close-out (91 – 120 days post last enrollment; reporting only required)
- Optional visits
 - Re-implant/Revision (as needed)
 - Any unscheduled visits or additional interim visits

In clinic visits that occur outside the specified visit window will be classified as "Unscheduled Visits". CIP visits that occur outside the specified visit window will be documented as a CIP deviation.

All data collected according to the Data Collection Requirements (Table 11-1) and specified in Sections 11.2 to 11.10 is to be appropriately noted in the eCRF.

Table 11-1: Data Collection Requirements

Procedure/Assessment	Enrollment and Consenting Clinic Visit (required) (≤ 30 days prior to implant procedure)	Implant Procedure (required) (Day 0) Re-implant/ Revision (as needed)	Follow- Up Visits				
			Pre-discharge Visit (required) (0-5 days post-implant procedure)	1 Month Visit (required) (30 ± 15 days post-implant procedure)	3 Month Visit (required) (91 ± 21 days post-implant procedure)	Unscheduled Visit (optional) (according to Center SOC or subject needs)	Latitude-based Close-out¹ (required) (91-120 days post last enrollment)
Informed Consent Form, including informed consent signature and date	X	--	--		--	--	--
Subject information, medical/device history	X	--	--		--	--	--
Clinical assessment	X			O	O	--	--
Implant of CRT-P and implant measurements		X					
12 lead ECG recording	SOC				SOC		
12 lead ECG recording upload	X	--			X	--	--
ECG 10s device based			X		X		
LV pacing threshold for all available vectors			X		X	--	
LVAT function (programming and documenting)		X	X		X	--	
LVAT data report			X		X	--	
Device assessment/interrogation Leads (impulse, threshold, sensing amplitude) MICS Header		X	X	X	X	--	
Manual confirmation of POST function/daily measurements		X	X	--	X	--	
Device programming			X	X	X		

Procedure/Assessment	Enrollment and Consenting Clinic Visit (required) (≤ 30 days prior to implant procedure)	Implant Procedure (required) (Day 0) Re-implant/ Revision (as needed)	Follow- Up Visits				
			Pre-discharge Visit (required) (0-5 days post-implant procedure)	1 Month Visit (required) (30 ± 15 days post-implant procedure)	3 Month Visit (required) (91 ± 21 days post-implant procedure)	Unscheduled Visit (optional) (according to Center SOC or subject needs)	Latitude-based Close-out¹ (required) (91-120 days post last enrollment)
6 minute walking test				X	X		
Device data collection (electronically) and electronic upload			X	X	X		
Manual threshold and device testing		X	X	X	X	--	
Current/concomitant medications ²	X		X	X	X		
Adverse device events ³ and SAEs	--	X	X	X	X	X	X
Latitude report on device data collection; battery status/diagnostic report			X	X	X	X	X

ECG=electrocardiogram; HF=heart failure; O=optional; POST=Post-Operative System Test; SAE=serious adverse event; SOC=standard of care; X=required; --=not required

1. A 12 month post-implant data collection will be done, but will be done remotely and does not require a site visit
2. Only heart failure medication classes (Beta blockers, ACE inhibitors, diuretics, etc.); currently being administered or changes to administration of.
3. To include collection of all USADEs, SADEs, ADEs, DDs; collection of all SAEs

11.2. Study Candidate Screening

After approval by the Investigator's Ethics Committee (EC) and the sponsor or delegated representative, the Investigator will follow standard of care (SOC) practices to screen subjects for inclusion in the study. Subjects are considered enrolled after they have met all inclusion criteria, none of the exclusion criteria, and provided written informed consent in accordance with applicable regulatory agency and EC requirements.

11.3. Informed Consent

During the Enrollment and Consenting Visit (Section 11.4) a qualified center representative will review the consent with a potential subject. The subject will be encouraged to ask any questions about the study. All questions from the subject should be addressed prior to the subject signing the informed consent. If the subject signs the informed consent, a signed copy should be provided to the subject and the original should be filed in the medical records. Documentation of the consent process by the person obtaining consent should be filed in the subject study file. Study personnel should explain to the subject that even if the subject agrees to participate in the study and signs the study Informed Consent Form (ICF), the implant procedure may demonstrate that the subject is not a suitable candidate for the study. No study-specific data collection of any procedure should be conducted prior to consent.

11.4. Enrollment Visit (≤ 30 days prior to implant procedure; required)

Prior to initiating any study procedures, the Investigator must ensure that appropriate informed consent has been documented (Section 11.3).

The data collection at enrollment includes: subject information and medical history; subject status and clinical assessment per SOC; and details on previously/currently implanted devices.

Baseline data that are not caught in the hospital records must be queried and documented with a Note to File.

Subject information and medical history

- **Demographic data:** age at time of consent; gender.
- **Additional rhythm disease:** information will be collected on additional relevant rhythm diseases: atrio-ventricular block; sinus node dysfunction; paroxysmal/chronic atrial fibrillation; chronotropic incompetence.
- **Subject etiology:** ischemic cardiomyopathy; idiopathic cardiomyopathy; valvular; cardiomyopathy; hypertrophic cardiomyopathy; congenital heart disease; infiltrative disease; neuromuscular disease (including myotonic dystrophy and Kearns-Sayre syndrome).
- **Associated diseases/risk factors:** hypertension, diabetes, renal disease, chronic pulmonary disease, peripheral artery disease, COPD, asthma, other known malignancies (tumor, lymphoma or leukemia), other chronic diseases.

- **Other subject history:** previous stroke; previous myocardial infarction; previous hospitalization for heart failure; previous ablation (AV node, atrial fibrillation or atrial flutter).
- **Current/concomitant medication:** documentation of current/concomitant medication classes being administered for treatment of heart failure

History of implanted devices

- **Pacemaker, ICD, etc. data:** Implant date, number of years implanted, model and manufacturer
- **Pacing lead data:** cardiac chamber (atrial and ventricular), number of years implanted and lead-model and manufacturer

Baseline subject status and clinical assessment

- **Clinical assessment data:** weight, height, blood pressure, New York Heart Association (NYHA) class, Left Ventricular Ejection Fraction (<1 year old).
- **Electrocardiogram (data collection and document upload in e.g. pdf format):** date (maximum 1 month before enrollment); rhythm (normal sinus rhythm, junctional rhythm, atrial fibrillation, paced); resting heart rate; intrinsic QRS width; intrinsic PR interval, intrinsic QT interval; QRS morphology (normal, right bundle branch block (RBBB), left bundle branch block (LBBB), other conduction disorders). The Investigator should classify the nature of the subjects intrinsic intra-ventricular conduction delay (e.g. LBBB, RBBB, or non-specific) per the World Health Organization Guidelines. These guidelines can be found in Appendix B: Ventricular Conduction Delay Definitions.

